## REVISION HISTORY

Revision	Date	Change
A	01MAR2020	Initial draft for IDE submission to FDA
B	22JUL2020	Revisions to address FDA feedback on original IDE G200131
C	07DEC2020	Revisions to address FDA feedback from Q-sub meeting Q201563/S001 on 15OCT2020
D	19FEB2021	Revisions to address FDA feedback from FDA conditional approval letter

## STATEMENT OF COMPLIANCE

The study will be conducted in accordance with the design and specific provisions of this Institutional Review Board (IRB)/ Ethics Committee (EC)/ Research Ethics Board (REB) approved protocol, in accordance with the ethical principles that have their origin in the Declaration of Helsinki, and that are consistent with International Conference of Harmonization (ICH) Guidelines for Good Clinical Practice (GCP), ISO14155:2011, ISO 13485:2016, 21 CFR Part 11, 21 CFR Part 50, 21 CFR Part 54, 21 CFR Part 56, 21 CFR 812, 21 CFR Part 820, 93/42/EEC MDD and the applicable local, state, or national regulatory/legal requirement(s). The Principal Investigators will assure that no deviation from, or changes to, the protocol will take place without prior agreement from the Sponsor and documented approval from the IRB/EC/REB, except where necessary to eliminate an immediate hazard(s) to the study subjects. The Principal Investigators will promptly report to the IRB/EC/REB and the Sponsor of any changes in research activity and all unanticipated problems involving risk to human subjects, or others, as required.

**LIST OF ABBREVIATIONS**

ADE	Adverse Device Effect
AE	Adverse Event
ASPECTS	Alberta Stroke program early CT score
AVM	Arteriovenous Malformation
CEC	Clinical Events Committee
CFR	Code of Federal Regulations
CIP	Clinical Investigation Plan
CRO	Contract Research Organization
CT	Computed Tomography
CTA	Computed Tomography Angiogram
DALYS	Disability-life adjusted years
DMC	Data Monitoring Committee
eCRF	Case Report Form
EDC	Electronic Data Capture
ENT	Embolization of New Territory
eTICI	Expanded Thrombolysis in Cerebrovascular Infarction
FDA	Food and Drug Administration
FMEA	Failure Mode and Effect Analysis
FPE	First Pass Effect
GCP	Good Clinical Practice
HI	Hemorrhagic infarct
IA t-PA	Intra-arterial tissue plasminogen activator
ICA	Internal Carotid Artery
ICF	Informed Consent Form
ICH	International Conference of Harmonization
ICH	Intracranial Hemorrhage
IDE	Investigational Device Exemption
IFU	Instructions for Use
ITT	Intention-to-treat
IV	Intravenous
IV t-PA	Intravenous tissue plasminogen activator
LAR	Legally Authorized Representative
LVO	Large vessel occlusion
MCA	Middle Cerebral Artery
mFPE	Modified First Pass Effect
MRA	Magnetic Resonance Angiogram
MRI	Magnetic Resonance Imaging
mRS	Modified Rankin Score
mTICI	modified Thrombolysis in Cerebrovascular Infarction

NIH	National Institutes of Health
NIHSS	National Institutes of Health Stroke Score
PH	Parenchymal hematoma
PI	Principal Investigator
PP	Per Protocol
PRSAE	Procedure Related Serious Adverse Event
PT	Preferred Term
PTAE	Pretreatment Adverse Event
RFA-A	Rankin Focused Assessment-Ambulation
RHV	Rotating Hemostasis Valve
SAE	Serious Adverse Event/Experience
SADE	Serious Adverse Device Effect
SIV	Site Initiation Visit
SOC	System Organ Class
SOP	Standard Operating Procedure
SQV	Site Qualification Visit
TEAE	Treatment Emergent Adverse Event
TFSO	Time from Stroke Onset
TICI	Thrombolysis in Cerebrovascular Infarction
TIMI	Thrombolysis in Myocardial Infarction
UADE	Unanticipated Adverse Device Effect
USADE	Unanticipated Serious Adverse Device Effect

Study Design	The study is designed as a prospective, multinational, randomized, parallel group-controlled, blinded, non-inferiority study.
Masking	Double (patient, outcomes assessor)
Treatment Arms	
Subjects who meet the inclusion criteria will be randomized in a 1:1 ratio to one of the following two treatment arms:
 
Arm one (1): Endovascular Treatment with Envi™-SR
 
Arm two (2): Endovascular Treatment with an FDA cleared device for treatment of acute ischemic stroke (Control Devices)

Study Objective	The study objective is to examine and compare clinical outcomes, as measured by Modified Rankin Scale (mRS) at 90 days ( $\pm$ 15 days) post treatment, and related performance characteristics of the Envi™-SR and concurrent parallel Control Devices currently cleared by the U.S. FDA for treatment of stroke.
Estimated Enrollment	Adaptive design with a target ITT sample size of 270 subjects (135 per arm) with a maximum of 560 subjects to be enrolled.

Sites	Up to 30 sites in United States, Canada, and Europe
Indications for Use	
Study Reports summarizing data from this investigation will be submitted to the FDA as part of an IDE application seeking the following indications for use:
 
 
1. The Envi™-SR is indicated for use to restore blood flow in the neurovasculature by removing thrombus for the treatment of acute ischemic stroke to reduce disability in patients with a persistent, proximal anterior circulation, large vessel occlusion, and smaller core infarcts who have first received intravenous tissue plasminogen activator (IV t-PA). Endovascular therapy with the device should be started within 6 hours of symptom onset.
 
2. The Envi™-SR is intended to restore blood flow in the neurovasculature by removing thrombus in patients experiencing ischemic stroke within 8 hours of symptom onset. Patients who are ineligible for IV t-PA or who fail IV t-PA therapy are candidates for treatment.
 
3. The Envi™-SR is indicated for use to restore blood flow in the neurovasculature by removing thrombus for the treatment of acute ischemic stroke to reduce disability in patients with a persistent, proximal anterior circulation, large vessel occlusion of the internal carotid artery (ICA) or middle cerebral artery (MCA)-M1 segments with smaller core infarcts (0-50 cc for age < 80 years, 0-20 cc for age ≥ 80 years). Endovascular therapy with the device should start within 6-24 hours of time last seen well in patients who are ineligible for intravenous tissue plasminogen activator (IV t-PA) or who fail IV t-PA therapy.
 

Device Description	The Envi™-SR is a self-expanding, nitinol stent-like mechanical thrombectomy device that is designed to be delivered to the neurovasculature through a microcatheter to retrieve thrombus.
Duration of Study	The total duration of the study is expected to be approximately 36-48 months
Duration of Subject Participation	Subjects will be in study for up to 90 days (± 15 days).
Primary Effectiveness Endpoint	The proportion of subjects with good clinical outcome defined as Modified Rankin Score (mRS) of ≤2 as assessed by a blinded assessor at 90 days (± 15 days).
Primary Safety Endpoint	Device-related or procedure-related symptomatic intracranial hemorrhage (sICH) defined by the Heidelberg Bleeding Classification at 24 hours (-8/+12 hours) (as read by the Core Lab and adjudicated by Clinical Events Committee (CEC)).

Safety Endpoints	
The following endpoints will be presented for each treatment arm as part of the safety analysis:
 
 
1. Symptomatic intracranial hemorrhage (sICH) defined by the Heidelberg Bleeding Classification post-procedure (as read by the Core Lab and adjudicated by the CEC).
 
2. Asymptomatic intracranial hemorrhages (aICH) defined by the Heidelberg Bleeding Classification within 24 (-8/+12) hours post procedure (as read by the Core Lab and adjudicated by the CEC).
 
3. Device and Procedure Related Serious Adverse Events (PRSAE) within seven (7) days (-2/+3 days) or discharge, whichever is sooner.
 
4. Device and Procedure Related Serious Adverse Events (PRSAE).
 
5. Device-related Serious Adverse Device Effects.
 
6. Procedure-related mortality at seven (7) days (-2/+3 days) or discharge, whichever is sooner.
 
7. Stroke-related mortality at 90 days (<math>\pm 15</math> days) post-procedure.
 
8. All-cause mortality at 90 days (<math>\pm 15</math> days) post-procedure.
 
9. Neurological deterioration – defined by an increase of four (4) points or more on the NIHSS score, at the time of diagnosis compared to immediately before worsening within seven (7) days (-2/+3 days) or discharge, whichever is sooner.
 

Secondary Effectiveness Endpoints	
The following secondary effectiveness endpoints will be described and compared between the two (2) treatment arms:
 
 
1. The first secondary effectiveness endpoint will be an assessment of the mRS shift from baseline at 90 days (<math>\pm 15</math> days) following the study index procedure.
 
2. The second secondary effectiveness endpoint will be an assessment of the proportion of subjects who achieve reperfusion measured using the expanded Thrombolysis in Cerebrovascular Infarction index (eTICI). Successful achievement of the endpoint is defined as achieving an eTICI score of 2b50 or greater [eTICI 2b50-3] in the target vessel following three or less passes of the randomized device (as adjudicated by Core Lab).
 
3. The third secondary effectiveness endpoint will be an assessment of the proportion of subjects in whom a successful First Pass Effect is achieved. Successful achievement of the endpoint is defined as achieving an eTICI First Pass Effect (FPE) defined as eTICI 2c-3 after a single pass (as adjudicated by Core Lab).
 
4. The fourth secondary effectiveness endpoint will be an assessment of the proportion of subjects in whom a successful Modified First Pass Effect is achieved. Successful achievement of the endpoint is defined as achieving an eTICI Modified First Pass Effect (mFPE) defined as eTICI 2b50-3 after a single pass (as adjudicated by Core Lab).
 
5. The fifth secondary effectiveness endpoint will be an assessment of the proportion of subjects with Early Response defined as a NIHSS drop of <math>\geq 10</math> points from baseline or NIHSS score 0 or 1 at seven (7) days (-2/+3 days) or discharge, whichever is sooner.
 

Pre-specified Tertiary (Exploratory) Endpoints	
The tertiary endpoints of the study will include, but are not limited to the following:
 
 
1. The first exploratory endpoint will be the proportion of subjects with excellent clinical outcome defined as Modified Rankin Score (mRS) of <math>\leq 1</math> as assessed by a blinded certified assessor at 90 days (<math>\pm 15</math> days) post treatment.
 
2. The second exploratory endpoint will be an assessment of reperfusion based on the multinomial eTICI score (as adjudicated by the Core Lab).
 
3. The third exploratory endpoint will be an assessment of the infarct growth as determined by the change in ASPECTS between baseline and 24 hours (<math>-8/+12</math> hours) post treatment (as adjudicated by the Core Lab).
 
4. The fourth exploratory endpoint will be an assessment of the infarct growth as determined by the change in lesion volumes measured by MR/CT perfusion imaging between baseline and 24 hours (<math>-8/+12</math> hours) post treatment (as adjudicated by the Core Lab, in subject subset with MR/CT perfusion imaging at 24 hours).
 
5. The fifth exploratory endpoint will be an assessment of final infarct volume at 24 hours (<math>-8/+12</math> hours) post treatment (as adjudicated by the Core Lab, in subject subset with MR/CT perfusion-weighted imaging at 24 hours).
 
6. The sixth exploratory endpoint will be an assessment of the time to restoration of flow (i.e. time from arterial puncture to initial restoration of flow; time from arterial puncture to eTICI 2b50 or better, time from first angiogram to initial restoration of flow, time from first angiogram to eTICI 2b50).
 
7. The seventh exploratory endpoint will be an assessment of Device Technical Success, defined as the proportion of devices with which successful delivery, deployment, and recapture of the randomized device is achieved.
 
8. The eighth exploratory endpoint will be an assessment of the number of passes to reperfusion of eTICI 2b50.
 
9. The ninth exploratory endpoint will be an assessment of the number of passes to final result.
 
10. The tenth exploratory endpoint will be an assessment of the number of passes to achieve reperfusion of eTICI 2b50 or greater (as adjudicated by the Core Lab).
 
11. The eleventh exploratory endpoint will be an assessment of the proportion of subjects who experience embolization of new territory (ENT) (as adjudicated by the Core Lab).
 
12. The twelfth exploratory endpoint will be an assessment of the proportion of subjects who experience embolization distal to the target occlusion (as adjudicated by the Core Lab).
 
13. The thirteenth exploratory endpoint will be the NIHSS Total Score as a continuous measure at each observation time point and change from baseline. NIHSS Total Score will be presented for the entire NIHSS scale and excluding scores on the Aphasia Subscale.
 
14. The fourteenth exploratory endpoint will be an assessment of the proportion of subjects with vessel patency based on MRA or CTA at 24 hours (<math>-8/+12</math> hours) post treatment (as adjudicated by the Core Lab, in subject subset with MRA/CTA imaging at 24 hours).
 

---	--

Inclusion Criteria	
 
1. Clinical signs consistent with acute ischemic stroke
 
2. Pre-stroke Modified Rankin Score <math>\leq 2</math>
 
3. Age 18 years and no upper limit (patient must be 18 years old at time of consent).
 
4. NIHSS <math>\geq 6</math> at the time of randomization
 
5. Subject is able to start treatment (defined as time of arterial puncture) within 24 hours of stroke onset or last known well and within 90 minutes from last baseline CT/ MRI.
 
6. Imaging: For strokes in the anterior circulation the following imaging criteria should also be met: 
 
a. If stroke onset (as defined by the time the patient was last seen at baseline) is within 6 hours: Baseline ASPECTS <math>\geq 6</math> on non-contrast CT (NCCT) or DWI-MRI;
 
b. If stroke onset is within 6-24 hours, advanced imaging with either CT perfusion or DWI-MRI is required. Baseline infarct volume must be <math>\leq 50</math>cc for patients under 80 years old and <math>\leq 20</math>cc for patients 80 years or older.
 
 
 
7. Location: Angiographic confirmation of an occlusion of an ICA (including T or L occlusions), M1 or M2 MCA, with eTICI flow of zero (0) – one (1).
 
8. Patients for whom IV t-PA is indicated are treated with IV t-PA without delay.
 
9. IV t-PA, if used, is initiated within three (3) hours of stroke onset (onset time is defined as the last time when the patient was witnessed to be at baseline), with investigator verification that the subject has received/is receiving the correct IV t-PA dose for the estimated weight.
 
10. Consent: The patient or the patient's legally authorized representative (LAR) has signed and dated an Informed Consent Form.
 
11. Will comply with protocol follow-up schedule.
 
12. Patient was ambulatory prior to stroke, i.e. able to walk without another person's assistance.
 

---------------------------	--

Exclusion Criteria	
 
1. Life expectancy likely less than six (6) months.
 
2. Females who are pregnant or breastfeeding.
 
3. Known history of severe allergy (more than rash) to contrast medium that cannot be medically controlled.
 
4. Suspicion of renal failure (Renal failure as defined by a serum creatinine >3.0 mg/dL (264 µmol/L) or Glomerular Filtration Rate (eGFR) <30).
 
5. Severe, sustained hypertension (Systolic Blood Pressure >185 mmHg or Diastolic Blood Pressure >110 mmHg) NOTE: If the blood pressure can be successfully reduced and maintained at the acceptable level using medication the subject can be enrolled.
 
6. Currently participating in another interventional (drug, device, etc.) research project that may confound the results of this study.
 
7. Known hereditary or acquired hemorrhagic diathesis, coagulation factor deficiency. (A subject without history or suspicion of coagulopathy does not require INR or prothrombin time lab results to be available prior to enrollment.)
 
8. Known history of platelet count <100,000/µL.
 
9. Baseline blood glucose of <50mg/dL (2.78 mmol) or >400mg/dL (22.20 mmol).
 
10. Subjects with occlusions in multiple vascular territories (e.g., bilateral anterior circulation, or anterior/posterior circulation).
 
11. CT or MR evidence of hemorrhage.
 
12. Seizures at stroke onset.
 
13. Suspicion of aortic dissection.
 
14. Patients with known hypersensitivity to nickel-titanium.
 
15. Evidence of dissection in the extra or intracranial cerebral arteries.
 
16. Stenosis, or any occlusion, in a proximal vessel that requires treatment or prevents access to the site of occlusion.
 
17. Presumed septic embolus, suspicion of bacterial endocarditis, or other serious infection.
 
18. Suspected cerebral vasculitis based on medical history and CTA/Magnetic Resonance Angiogram (MRA).
 
19. Excessive vascular access tortuosity that will likely prevent endovascular access.
 
20. Baseline CT or Magnetic Resonance Imaging (MRI) showing intracranial tumor (except asymptomatic small meningiomas less than three (3) cm).
 
21. Significant mass effect with midline shift
 
22. Treatment with any cleared thrombectomy devices or other intra-arterial (neurovascular) therapies three months prior to use of treatment device
 
23. Unlikely to be available for 90-day (± 15 days) follow-up (e.g. no fixed home address, visitor from overseas).
 
24. Rapid neurological improvement prior to study enrollment suggesting resolution of signs/symptoms of stroke such as a decrease that leads to an NIHSS below the study cut-off of six (6).
 
25. Patient has suffered a hemorrhagic or ischemic stroke or TIA in at least the last three (3) months.
 
26. Patients with a pre-existing neurological or psychiatric disease that would confound the neurological or functional evaluations, mRS score at baseline must be ≤ 2. This excludes patients who are severely demented, require constant assistance in a nursing home type setting or who live at home but are not fully independent in activities of daily living (toileting, dressing, eating, cooking and preparing meals, etc.).
 
27. Known cancer with metastases.
 
28. Subject currently uses or has a recent history of illicit drug(s), which includes marijuana.
 
29. Recent past history (within three (3) months) or clinical presentation of intracranial hemorrhage (ICH), subarachnoid hemorrhage (SAH), ruptured arteriovenous malformation (AVM) or ruptured aneurysm.
 

---------------------------	--

	30.The patient is in a coma.
--	------------------------------

Statistics	
This prospective, multi-center randomized adaptive clinical study is composed of three (3) phases: screening, procedure, and follow-up. The analyses to address the primary and secondary objectives will be based on the data collected during the procedure and follow-up period. There is a single primary effectiveness endpoint and a primary safety endpoint. There are five (5) secondary endpoints that will be evaluated statistically in hierarchical order. The results from the fourteen tertiary endpoints will be summarized and compared between the two (2) randomized treatment arms as supportive information.
 
The non-inferiority margins for the primary and secondary endpoints come from five (5) published reference studies using retrieval devices in a similar subject population. Where a non-inferiority margin is not available from the peer-reviewed literature, the confidence limit of the difference (Envi™-SR minus Control) in the proportion of subjects experiencing the event of interest, establishing non-inferiority will require zero to be contained within the 1-sided 97.5% or 2-sided 95% confidence limits.
 
The target Intention to Treat (ITT) sample size for this clinical investigation is 270 subjects: 135 subjects per arm. An interim assessment based on conditional power (CP) will be performed by the independent Data Monitoring Committee (DMC) after 50% of the target ITT enrollment (135 subjects) has been randomized and either completed the 90-day (<math>\pm 15</math> days) evaluation visit or withdrawn prematurely. The interim assessment may result in the target enrollment being increased to a maximum of 560 subjects consented and enrolled. Following the interim assessment, the DMC will provide a non-binding recommendation to the sponsor to either continue enrolling to the target sample size, increase enrollment up to the maximum sample size, or stop the study for futility (<math>CP < 37\%</math>).
 
At the time of the interim assessment performed by the DMC, the Committee will receive data on all adverse events, effectiveness, investigational site, time last seen well (TLSW), and Additional Therapy for each patient. Through inspection of the tabulated data the DMC will be tasked with examining if data are consistent with planning estimates as described in the DMC Charter.
 
The Intention to Treat (ITT) population will include all subjects that have signed the informed consent form (ICF) and were randomized. The primary population for the primary and secondary analyses for this study will be the ITT population. The ITT population will also serve as the Safety population.
 
Randomization to either Envi™-SR or Control will be performed in a 1:1 ratio, stratified by six (6) factors using a dynamic randomization scheme:
 
 
• Age: <math>\geq 67</math> and <math>< 67</math>
 
• Site of occlusion: ICA, MCA M1, MCA M2
 
• Baseline/Enrollment NIHSS score: <math>< 17</math> and <math>\geq 17</math>
 
• Prior IV t-PA usage: Yes and No
 
• Time to symptom onset: <math>\geq 6</math> hours and <math>< 6</math> hours
 
• Baseline ASPECTS: 6-7 and 8-10
 
 
This randomized study will ensure that the assessing clinical team are blinded to treatment assignment. Due to the nature of the treatment, and access to the patient records, the treatment team is not required to be blinded. The treatment team will obtain a randomization assignment using a web-based randomization system.
 
The primary effectiveness and safety endpoints will be evaluated simultaneously. If the primary effectiveness endpoint is met (Envi™-SR non-inferior to Control), the secondary effectiveness endpoints will be evaluated statistically in the hierarchical order presented in this protocol and the Statistical Analysis Plan (SAP).

-------------------	--

	
The primary effectiveness endpoint is an assessment of global disability assessed via the blinded evaluation by the assessing clinical team of the proportion of subjects with a Modified Rankin Scale (mRS) <math>\leq 2</math> recorded 90 days (<math>\pm 15</math> days) after the study index procedure. The proportions will be compared between the Envi™-SR and Control device arms. The variability between and within the five (5) peer-reviewed reference studies serves as the basis for establishing the non-inferiority margin for this endpoint.
 
The primary effectiveness endpoint will be derived three (3) ways:
 
Method 1: mRS based on the observed results, independent of the use of additional therapies to retrieve the clot. Multiple imputation will be used to impute the mRS score for patients who become lost to follow-up prior to the 90 day evaluation.
 
Method 2: mRS based on the observed results for patients where additional therapies were not used to retrieve the clot. Patients who required additional therapy for reperfusion failure or additional off-label therapies to retrieve the clot will be automatically treated as primary effectiveness endpoint failures. Multiple imputation will be used to impute the mRS score for patients who become lost to follow-up prior to the 90 day evaluation.
 
Method 3: mRS based on the observed results for patients where additional therapies were not used to retrieve the clot. Subjects who required any additional therapy, either on label or off-label, to retrieve the clot will be automatically treated as primary effectiveness endpoint failures. Multiple imputation will be used to impute the mRS score for patients who become lost to follow-up prior to the 90 day evaluation.
 
Method 1 is the primary method for the derivation of the primary effectiveness endpoint for the study; Method 2 and Method 3 represent secondary derivations of the primary effectiveness endpoint.
 
The non-inferiority margin for the primary effectiveness endpoint has been pre-specified at 12.5%. The primary effectiveness analysis will be based on the lower bound of the 1-sided 97.5% confidence interval of the difference (Envi™-SR minus Control) in global disability. If the lower bound is numerically greater than -12.5%, Envi™-SR will be considered non-inferior to Control.
 
The primary safety endpoint is an assessment of device-related or procedure-related symptomatic intracranial hemorrhage (sICH) within 24 hours (-8/+12 hours) (as read by the Core Lab and adjudicated by CEC) of the study index procedure. The incidence of sICH is not expected to exceed 4% in either arm of the study. If the upper bound of the 1-sided 97.5% confidence interval of the difference (Envi™-SR minus Control) in sICH is numerically less than 7%, Envi™-SR will be considered non-inferior to Control.

--	--

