### 8.3.2. Analysis of the Secondary and Tertiary Endpoints

If non-inferiority is achieved based on the primary endpoint, a hierarchical step-down approach will be used to test the secondary endpoints in rank order. The following secondary effectiveness endpoints will be compared between the two treatment arms:

1. The first secondary effectiveness endpoint will be an assessment of the mRS shift from baseline at 90 days ( $\pm 15$  days) following the study index procedure. The Cochran–Mantel–

Haenszel test will be used to derive the 95% confidence intervals for the overall odds ratio. If the 95% confidence intervals for the overall odds ratio does not contain 1, the conclusion will be that the mRS shift is not proportional between the 2 devices. This is a 2-sided evaluation of the odds ratio.

2. The second secondary effectiveness endpoint will be an assessment of the proportion of patients who achieve reperfusion measured using the expanded Thrombolysis in Cerebrovascular Infarction index (eTICI). Successful achievement of the endpoint is defined as achieving an eTICI score of 2b50 or greater [eTICI 2b50-3] in the target vessel following three or less passes of the randomized device (as adjudicated by Core Lab). If the lower bound of the 1-sided 97.5% confidence interval of the difference (Envi™-SR minus Control) in the proportion of patients with eTICI 2b50 or greater flow in the target vessel post-procedure is numerically greater than -12.1%, Envi™-SR will be considered non-inferior to Control. This is a 1-sided evaluation to establish non-inferiority.
3. The third secondary effectiveness endpoint will be an assessment of the proportion of patients in whom a successful First Pass Effect is achieved. Successful achievement of the endpoint is defined as achieving an eTICI First Pass Effect (FPE) defined as eTICI 2c-3 after a single pass (as adjudicated by Core Lab). If the lower bound of the 1-sided 97.5% confidence interval of the difference (Envi™-SR minus Control) in the proportion of patients with eTICI 2c or greater flow in the target vessel post- first pass is numerically greater than -12.1%, Envi™-SR will be considered non-inferior to Control. This is a 1-sided evaluation to establish non-inferiority.

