4. The fourth secondary effectiveness endpoint will be an assessment of the proportion of patients in whom a successful Modified First Pass Effect is achieved. Successful achievement of the endpoint is defined as achieving an eTICI Modified First Pass Effect (mFPE) defined as eTICI 2b50-3 after a single pass (as adjudicated by Core Lab). If the lower bound of the 1-sided 97.5% confidence interval of the difference (Envi™-SR minus Control) in the proportion of patients with eTICI 2b50 or greater flow in the target vessel post- first pass is numerically greater than -12.1%, Envi™-SR will be considered non-inferior to Control. This is a 1-sided evaluation to establish non-inferiority.
5. The fifth secondary effectiveness endpoint will be an assessment of the proportion of subjects with Early Response defined as a NIHSS drop of  $\geq 10$  points from baseline or NIHSS score 0 or 1 at seven (7) days (-2/+3 days) or discharge, whichever is sooner. If the probability value from the 2-tailed Fisher's exact test is  $< 0.05$  and the proportion of patients with an NIHSS of 0 or 1, or improvement in the NIHSS of 10 points or more from the baseline (pre-procedure) score is greater in the Envi™-SR treatment arm compared to the control arm, the null hypothesis will be rejected and Envi™-SR will be considered superior to Control. This is a 2-sided evaluation of the proportions.

The details for analyzing the individual tertiary endpoints are presented in the SAP.

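### The fallback that reads zero inside the interval as non-inferiority is not a non-inferiority test and conflicts with the Early Response rule; mRS shift, first in the hierarchy, has no direction, margin or pass criterion

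*Combined protocol and SAP*

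**What the plan says.** The Protocol Synopsis (Statistics) covers endpoints for which the literature supplies no margin. It refers to the difference between arms in the proportion with the event and states that "establishing non-inferiority will require zero to be contained within the 1-sided 97.5% or 2-sided 95% confidence limits". It also says: "There are five (5) secondary endpoints that will be evaluated statistically in hierarchical order".

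Section 8.3.2 repeats that, once the primary endpoint has shown non-inferiority, "a hierarchical step-down approach will be used to test the secondary endpoints in rank order". The five steps have these rules:

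- **Step 1, mRS shift at 90 days.** Analysed by the Cochran–Mantel–Haenszel method, with one stated rule: "If the 95% confidence intervals for the overall odds ratio does not contain 1, the conclusion will be that the mRS shift is not proportional". Here one device is compared with the other, and the section then gives the sidedness: "This is a 2-sided evaluation of the odds ratio".
- **Steps 2 to 4, eTICI 2b50-3 within three passes, First Pass Effect and modified First Pass Effect.** Each succeeds if the lower bound of the one-sided 97.5% interval "is numerically greater than -12.1%, Envi™-SR will be considered non-inferior to Control".
- **Step 5, Early Response.** No margin. If the two-tailed Fisher p-value is below 0.05 and the proportion is greater with Envi-SR, "the null hypothesis will be rejected and Envi™-SR will be considered superior to Control".

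**The concern.** There are two separate faults.

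First, an interval that contains zero shows only that no difference was detected. Non-inferiority needs the interval to exclude a stated loss. Without that, a wider interval makes success easier, and a device whose interval lies wholly above zero fails. For Early Response the synopsis and Section 8.3.2 also give incompatible routes to success: an interval containing zero would support a non-inferiority claim under one and be a failed superiority test under the other.

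Second, a step-down procedure controls error only if each step has a defined pass. Step 1 says what is concluded when the interval excludes 1, but not whether that is success, nor in which direction. The conclusion it draws is also wrong: an odds ratio different from 1 means that the distribution has shifted towards one arm. Proportionality is a different question, namely whether the odds ratio is the same at every cut of the scale. At stake is which secondary claims, including the three reperfusion claims, can be made formally.

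**Working it through.** **The plan's own sample size.** Inputs from Section 8.2: 46% against 50.5%, margin 12.5 points, one-sided 2.5%. The 80% power is stated only beside the maximum sample size and is assumed here for the target.

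- Target, per arm: (1.960 + 0.842)² × (0.46×0.54 + 0.505×0.495) / (0.045 + 0.125)² = 7.849 × 0.4984 / 0.0289 = 135.4, or 272 in total. The plan states 270.
- At 49.5% against 50.5%: 7.849 × 0.49995 / 0.135² = 215.3 per arm, or 432 in total. The plan states 426.

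Both agree to within 2%, so the planning inputs are understood correctly. The checks below use 135 per arm (270) and 224 per arm (448, the maximum ITT size).

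**Fallback rule.** With true difference d and SE = √[(pC(1−pC) + pE(1−pE))/n], the two-sided 95% interval contains zero with probability Φ(1.96 − |d|/SE), ignoring a negligible far tail. The documents give no Early Response rate, so the control rate is an assumption, varied from 30 to 70%. The 12.5-point loss is borrowed from the primary margin.

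| Truth: Envi-SR 12.5 points worse | 135 per arm | 224 per arm |
|---|---|---|
| Control 30% | 32% pass | 12% pass |
| Control 50% | 45% pass | 23% pass |
| Control 70% | 42% pass | 21% pass |

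Example: control 50%, n = 135. SE = √[(0.25 + 0.2344)/135] = 0.0599; 0.125/0.0599 = 2.087; Φ(1.96 − 2.087) = 0.45. A valid test with a 12.5-point margin would pass this device 2.5% of the time.

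Imprecision is rewarded: at a 50% control rate the pass rate is 69% with 67 per arm, 45% with 135 and 23% with 224. Benefit is penalised: if Envi-SR is truly 10 points better (60% against 50%), SE = 0.0602 at 135 per arm, Φ(1.96 − 1.660) = 0.62, and the rule fails it 38% of the time; at 224 per arm it fails 57%. The synopsis also allows a one-sided 97.5% interval without saying which bound. If that means a lower bound only, zero is contained whenever the bound is at or below zero, and the device 12.5 points worse passes almost always.

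**mRS shift.** The planning rates give an odds ratio of (0.505/0.495)/(0.46/0.54) = 1.20, log 0.180. Under proportional odds, var(log OR) = 12/[N(1 − Σp³)]. The documents give no full mRS distribution. I assumed shares of 0.10, 0.17, 0.19, 0.17, 0.16, 0.06 and 0.15 for scores 0 to 6 (46% at 0 to 2), so 1 − Σp³ = 0.975.

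- N = 270: SE = √(12/263.2) = 0.2135; z = 0.845; Φ(0.845 − 1.96) = 13%.
- N = 448: SE = √(12/436.6) = 0.1658; z = 1.088; Φ(1.088 − 1.96) = 19%.
- Varying 1 − Σp³ from 0.75 to 0.98 gives 11 to 13% and 16 to 19%.

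Step 1 is reached only after the primary passes on the same 90-day mRS. Simulating both tests on the assumed distribution gives the chance that the interval excludes 1, given primary non-inferiority:

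| True effect | 135 per arm | 224 per arm |
|---|---|---|
| Equal devices | 5% | 3% |
| OR 1.20 (46% against 50.5%) | 17% | 20% |

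If excluding 1 is the pass, the step blocks the three margin tests about 95 to 97% of the time with equal devices and 80 to 83% at the planned advantage. If containing 1 is the pass, those same percentages become the pass rates, and the step has the fallback's fault.

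**The case against.** Several stronger readings are tempting and are not supported.

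- *No endpoint without a margin has a valid rule.* Early Response does: a directional superiority test in Section 8.3.2. Its fault is the conflict with the synopsis.
- *The synopsis fallback and the mRS-shift rule are opposites.* The fallback is worded for a difference in proportions, so it does not literally govern an odds ratio. Nor is any step in the hierarchy clearly governed by it, since steps 2 to 4 have margins and step 5 has its own rule.
- *The fallback passes a clearly worse device.* A significantly worse device has a two-sided interval wholly below zero and fails. What passes is a real loss that the data were too imprecise to show.
- *The hierarchy will almost surely stop at step 1.* That depends on a pass criterion the protocol does not state. Even on that criterion, blocking at the planned advantage is likely rather than near certain.
- *The gate could open because Control is better.* After the primary has passed, this is practically excluded: about 0.02% or less with equal devices, and under 0.4% at a log odds ratio of −0.2.

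The protocol also defers detail to the SAP. No separate SAP text was in the material reviewed, so a pass rule there cannot be ruled out. What stands is that the fallback sentence is wrong as written, that it conflicts with Section 8.3.2, and that Section 8.3.2 does not define success for its first step.

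**Conclusion.** The concern holds in this limited form. The fallback is not a non-inferiority criterion: it passes a device 12.5 points worse 32 to 45% of the time at 135 per arm and 12 to 23% at 224, under assumed control rates of 30 to 70% and the two-sided interval. Its practical reach is narrow, because the only proportion in the hierarchy it could touch is Early Response, where it contradicts the superiority rule.

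The mRS-shift step is under-specified. Its chance of success, given a passed primary, runs from about 3 to 20% on one reading to about 80 to 97% on the other, across the two scenarios and two sample sizes. Those figures rest on an assumed mRS distribution and proportional odds. The absence of a pass rule needs no assumption.

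The primary effectiveness and safety tests and the sample size are not affected. This should be fixed, but it bears on secondary claims only.

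**What to change.** 1. Delete the fallback sentence from the synopsis. Report any endpoint without a pre-specified margin as an estimate with its confidence interval and no non-inferiority claim.
2. Reconcile the synopsis with Section 8.3.2, so that Early Response is tested for superiority only.
3. Give mRS shift an explicit directional pass rule in both protocol and SAP before unblinding. Either superiority, with the lower 95% limit of the common odds ratio above 1 in Envi-SR's favour, or non-inferiority against a pre-specified and justified odds-ratio margin.
4. Replace the conclusion about proportionality with a statement about the direction and size of the shift.

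If mRS shift stays a superiority test, the sponsor may place it behind the three margin tests so that it does not block them. Ranking reperfusion ahead of function is a matter of priority and remains the sponsor's choice.

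Items 1 to 4 need only a wording amendment to protocol and SAP, with no extra patients or data, although an odds-ratio margin would need its own justification. Changing the order alters a pre-specified hierarchy in a protocol already revised after regulatory feedback, so it may need further agreement.
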